8.2.3 General Statistical Consideration

8.2.3.1 All statistical analyses will be performed for intent-to-treatment population.

8.2.3.2 The survival estimates will be derived from Kaplan and Meier curves.

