3.2 Secondary Objective(s) & Hypothesis(es)

The study will also explore other efficacy endpoints and safety of adjuvant pembrolizumab in locally advanced ESCC patients who have high risk of recurrence following preoperative CRT and esophagectomy.

(1) Objective:

- a. To improve the median RFS, compared with historical control.
- b. To improve the 3-year RFS rate, compared with historical control
- c. To improve the 3-year overall survival (OS) rate, compared with historical control.
- d. To improve the median OS, compared with historical control.
- e. To determine the toxicity and safety.

(2) Hypothesis:

- a. In addition to improving the 1-year RFS rate, the addition of pembrolizumab to adjuvant cisplatin- CRT would improve median RFS in locally advanced ESCC patients who have high risk of recurrence following preoperative CRT and esophagectomy.
- b. In addition to improving the 1-year RFS rate and the median RFS, the addition of pembrolizumab to adjuvant cisplatin- CRT would also improve the 3-year RFS rate in locally advanced ESCC patients who have high risk of recurrence following preoperative CRT and esophagectomy.

- c. The addition of pembrolizumab to adjuvant cisplatin- CRT would improve the OS, through reducing the recurrence rates, of locally advanced ESCC patients who have high risk of recurrence following preoperative CRT and esophagectomy.
- d. In addition to improving 3-year OS rate, the addition of pembrolizumab to adjuvant cisplatin- CRT would also improve the median OS in locally advanced ESCC patients who have high risk of recurrence following preoperative CRT and esophagectomy.
- e. The addition of pembrolizumab to adjuvant cisplatin- CRT is safe and does not result in significant toxicities in locally advanced ESCC patients who have high risk of recurrence following preoperative CRT and esophagectomy.

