5.2 Trial Treatments

The treatment to be used in this trial is outlined below in Table 2.

Table 2 Trial Treatment

Drug or radiotherapy	Dose/Potency	Dose Frequency	Route of Administration	Regimen/Treatment Period	Use
Cisplatin	30 mg/m ²	QW	IV infusion	Day 1 of each week for 2 weeks, starting within 8 weeks after esophagectomy.	Adjuvant CRT
Radiotherapy	180-200 cGy	QD (Monday to Friday)		Total 10-13 fractions	Adjuvant CRT
Pembrolizumab	200 mg	Q3W	IV infusion	Day 1 of each 3 week cycle for 18 cycles, starting within 4 weeks after completing adjuvant cisplatin-CRT	Experimental

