5.2.2 Timing of Dose Administration

5.2.2.1 Cisplatin-CRT:

- a. Cisplatin-CRT is to be started within 8-12 weeks after esophagectomy, when the patient recovers well from the operation.
- b. Cisplatin 30 mg/m², IV infusion for 60~ 120 min, weekly, for 2 weeks.
 - i. Sufficient hydration will be given at the discretion of the investigator.
 - ii. Anti-emetics such as 5-HT3 antagonists, aprepitant, steroid, and metoclopramide will be given at the discretion of the investigator.
- c. Radiotherapy: (intensity modulated radiotherapy) 180-200 cGy/fraction, once daily, 5 days a week, for a total of 10-13 fractions.
 - i. Radiotherapy will be administered by megavoltage linear accelerators (\geq 6 MV photon) using multiple fields (\geq 2) technique.
 - ii. Planning CT (CT simulation) must be done for isodose distribution and evaluation of dose-volume histogram.
 - iii. The target volumes of radiation should encompass the tumor volume (both primary esophageal tumor and metastatic lymphadenopathy) with adequate margins covering subclinical disease (including submucosal, mediastinal, and/or supraclavicular or celiac lymphatics) and treatment variability (including setup errors, breathing, and organ motion). Gross tumor volume (GTV) is defined as the volume of all visible esophageal tumor and involved lymphadenopathy using all available imaging studies including CT scan, EUS, and 18F-FDG-PET scan. The clinical target volume (CTV) is defined as the

GTV plus areas considered at significant risk of microscopic disease including a 0.5-1.0cm circumferential margin and 3-4 cm longitudinal margin.

- iv. Radiation will be delivered with intensity modulated radiotherapy technique, with a daily fraction size of 180-200 cGy, 5 days a week.

5.2.2.2 Pembrolizumab:

- a. Pembrolizumab is to be started within 4 weeks after completing last dose of CRT, when the patient recovers well from the CRT.
- b. Pembrolizumab should be administered on Day 1 of each cycle after all procedures/assessments have been completed as detailed on the Trial Flow Chart (Section 6.0). Trial treatment may be administered up to 3 days before or after the scheduled Day 1 of each cycle due to administrative reasons.
- c. Pembrolizumab will be administered on an outpatient basis.

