8.2 Statistical Analysis Plan

8.2.1 Sample Size Determination

According to the subgroup analysis of our previous study [12], the median RFS for locally advanced ESCC patients who have received preoperative cisplatin-based CRT followed by surgery, and exhibit high risk of tumor recurrence (defined as closed or involved margin [$\leq 1\text{mm}$] or ENI or ypN2-3) is 6.7 months, equivalent to a 1-year RFS rate of 32.3%. It would need a sample size of 24 patients to detect a difference of the 1-year RFS rate from 32% to 60% by calculated using an exact binomial test with a power of 80% and a 5% significance level. Having taken an additional 10% of early drop-out rate into consideration, the total enrolled patient number will be 26 for this study. We estimate an enrollment rate of 12 patients per year at my center. Therefore, total study period will be 5 years, including 2 years of patient enrollment and 3 years of patient follow-up.

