8.2.2 Definition of Variables

8.2.2.1 Recurrence-free survival is the time from enrollment to disease recurrence or the last follow-up (censored). Recurrence is defined by suspicious lesion noted by tumor imaging according to RECIST 1.1. Tissue proof for suspicious lesion is recommended if it is feasible.

8.2.2.2 Overall survival is the time from enrollment to death of any cause or the last follow-up (censored).

8.2.2.3 Evaluation of Toxicity: The incidence and severity of toxicity will be summarized according to the NCI Common Toxicity Criteria Version 4.0.

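### The intention-to-treat rule covers toxicity too, so patients who never start pembrolizumab would dilute the toxicity rates attributed to it

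*Combined protocol and SAP*

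**What the plan says.** Item 8.2.3.1 of the SAP sets one population for everything: "All statistical analyses will be performed for intent-to-treatment population". That population is not defined further. I take it to be all 26 enrolled patients.

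Item 8.2.2.3, just before it, makes toxicity an SAP variable without giving it a population of its own: "The incidence and severity of toxicity will be summarized according to the NCI Common Toxicity Criteria Version 4.0".

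Section 3.2 lists safety as a secondary objective ("To determine the toxicity and safety") and attaches a hypothesis to the added drug: "The addition of pembrolizumab to adjuvant cisplatin- CRT is safe and does not result in significant toxicities".

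The regimen is sequential. Table 2 in section 5.2 has pembrolizumab "starting within 4 weeks after completing adjuvant cisplatin-CRT", and section 5.2.2.2 makes the start conditional on the patient's condition: "Pembrolizumab is to be started within 4 weeks after completing last dose of CRT, when the patient recovers well from the CRT".

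The trial summary (section 1.0) lets treatment end at any point for recurrence, unacceptable toxicity, intercurrent illness or withdrawal. Section 8.2.1 allows for loss: "Having taken an additional 10% of early drop-out rate into consideration, the total enrolled patient number will be 26 for this study". Section 5.9 says that no one is replaced.

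**The concern.** Intention to treat protects an efficacy estimate from selective loss. Applied to harm, it counts patients who could not have had the event. In a sequential regimen some such patients are foreseeable: those who relapse, withdraw or do not recover from CRT before the first pembrolizumab dose.

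For pembrolizumab-attributed events the error runs one way only. Each never-exposed patient adds one to the denominator and nothing to the numerator, so the reported rate falls. That favours the section 3.2 hypothesis on the safety of adding pembrolizumab, and there is no control arm in which a similar dilution would offset it. An analyst who follows the SAP as written produces this rate. One who uses exposed patients departs from the SAP and chooses the denominator after the data are in.

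**Working it through.** **The plan's own figure.** Inputs: 1-year RFS of 32% against 60%, exact binomial test, 80% power, 5% level (section 8.2.1), two-sided (section 2.1). With n = 24 and success declared at 13 or more relapse-free patients, the upper-tail probability at 32% is 0.0202 (limit 0.025) and the power at 60% is 0.787, so 24 is reproduced closely. Adding 10% gives 24 × 1.10 = 26.4, stated as 26. These 26 patients are the denominator under the written rule.

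**Planned early loss.** The plan implies 26 − 24 = 2 patients, or 10% of 26 = 2.6, rounded up to 3. It does not say whether they leave before or after the first pembrolizumab dose.

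**Dilution.** Let k be the number of enrolled patients who never receive pembrolizumab. For an event that only pembrolizumab can cause:

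rate on all enrolled = rate in exposed patients × (26 − k)/26

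The relative understatement is k/26. The documents do not give k, so the table shows a range. The 30% true rate and the count of five affected patients are illustrations.

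| k | (26 − k)/26 | Relative understatement | True 30% is reported as | Five affected: all enrolled → exposed |
|---|---|---|---|---|
| 0 | 1.000 | 0% | 30.0% | 5/26 = 19.2% → 5/26 = 19.2% |
| 2 | 0.923 | 7.7% | 27.7% | 5/26 = 19.2% → 5/24 = 20.8% |
| 3 | 0.885 | 11.5% | 26.5% | 5/26 = 19.2% → 5/23 = 21.7% |

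With five affected patients the difference is 1.6 percentage points at k = 2 and 2.5 at k = 3. The exact 95% interval for 5/26 is 6.6% to 39.4%. The upper limit becomes 42.2% for 5/24 and 43.7% for 5/23.

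**Whole-regimen toxicity.** Adverse events are collected from treatment allocation, before CRT (section 7.2). Nearly every enrolled patient should receive some CRT, so the enrolled and treated denominators almost coincide for this summary.

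**The case against.** The case for leaving the text alone has several parts.

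- *The dilution may be zero.* This stands. If every enrolled patient receives one dose, nothing changes, and section 8.2.1 does not place the drop-outs before that dose.
- *The SAP names no pembrolizumab-specific rate.* True: item 8.2.2.3 plans only incidence and severity, and no toxicity threshold or test exists, so no formal decision can flip. But the section 3.2 hypothesis is about adding pembrolizumab, and it cannot be addressed without such a rate.
- *Summarising toxicity is description, not statistical analysis.* On that reading the plan gives a secondary objective no denominator at all, and the same amendment is needed.
- *Section 10.6 promises listings of premature terminations with dates and reasons.* These help a reader to reconstruct an exposed-patient rate, but they do not set the denominator of the reported one.
- *The shift is small beside the sampling error.* This also stands: 1.6 to 2.5 points against an interval about 33 points wide. Imprecision does not justify keeping a bias that is easily avoided.

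In the other direction, a reader might infer a larger effect from the historical RFS in section 8.2.1. A Weibull curve through 50% at 6.7 months and 32.3% at 12 months puts 18% of patients, 4.7 of 26, in relapse by week 6.6, and five never exposed would mean a 19% understatement. The documents do not support this:

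- The time origin of the historical RFS is not given.
- Week 6.6 assumes 13 uninterrupted fractions (2.6 weeks) plus the whole 4-week allowance.
- Recurrence is defined on imaging (item 8.2.2.1), and the flow chart (section 6.1) schedules none between screening and pembrolizumab cycle 4. Relapses in that window would come to light only through unscheduled imaging, and patients with undetected relapse could still be dosed.

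**Conclusion.** The point holds in a limited, conditional form. As written, the SAP puts pembrolizumab-attributed toxicity on a denominator that includes anyone who never received the drug, and any resulting error favours the safety hypothesis. The relative understatement is 0% if all patients are exposed and about 8% to 12% if the 2 to 3 planned early drop-outs all leave before the first dose. This rests on two assumptions: that the ITT population is all 26 enrolled, and that the drop-outs occur in that window.

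A reader might also infer that all toxicity results are understated, or that the trial would wrongly declare pembrolizumab safe. Neither follows: whole-regimen toxicity is little affected, and no formal safety criterion exists to be met. The primary endpoint and sample size are untouched.

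**What to change.** Limit item 8.2.3.1 to efficacy (RFS and OS), and add wording such as: 'Overall toxicity will be summarised in patients who received any study treatment. Pembrolizumab-phase toxicity (onset on or after the first pembrolizumab dose) and immune-related toxicity will be summarised in patients who received at least one pembrolizumab dose.' State the number in each set beside the rates. Exact 95% confidence intervals would be useful at this sample size but are optional; the correction does not depend on them.

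The cost is two or three sentences in the SAP, with no new data and no change to enrolment. The downside is that reported pembrolizumab toxicity rates may become slightly less favourable, with slightly wider intervals.

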9.0 LABELING, PACKAGING, STORAGE AND RETURN OF CLINICAL SUPPLIES

9.1 Investigational Product

The investigator shall take responsibility for and shall take all steps to maintain appropriate records and ensure appropriate supply, storage, handling, distribution and usage of investigational product in accordance with the protocol and any applicable laws and regulations.

Clinical Supplies will be provided by Merck as summarized in Table 7.

Table 7 Product Descriptions

Product Name & Potency	Dosage Form
Pembrolizumab 50 mg	Lyophilized Powder for Injection
Pembrolizumab 100 mg/ 4mL	Solution for Injection

9.2 Packaging and Labeling Information

Clinical supplies will be affixed with a clinical label in accordance with regulatory requirements.

9.3 Clinical Supplies Disclosure

This trial is open-label; therefore, the subject, the trial site personnel, the Sponsor and/or designee are not blinded to treatment. Drug identity (name, strength) is included in the label text; random code/disclosure envelopes or lists are not provided.

9.4 Storage and Handling Requirements

Clinical supplies must be stored in a secure, limited-access location under the storage conditions specified on the label.

Receipt and dispensing of trial medication must be recorded by an authorized person at the trial site.

Clinical supplies may not be used for any purpose other than that stated in the protocol.

9.5 Returns and Reconciliation

The investigator is responsible for keeping accurate records of the clinical supplies received from Merck or designee, the amount dispensed to and returned by the subjects and the amount remaining at the conclusion of the trial.

Upon completion or termination of the study, all unused and/or partially used investigational product will be destroyed at the site per institutional policy. It is the Investigator's responsibility to arrange for disposal of all empty containers, provided that procedures for proper disposal have been established according to applicable federal, state, local and institutional guidelines and procedures, and provided that appropriate records of disposal are kept.

10.2 Compliance with Financial Disclosure Requirements

Following the regulations of NTUH

10.3 Compliance with Law, Audit and Debarment

By signing this protocol, the investigator agrees to conduct the trial in an efficient and diligent manner and in conformance with this protocol; generally accepted standards of Good Clinical Practice (e.g., International Conference on Harmonization of Technical Requirements for Registration of Pharmaceuticals for Human Use Good Clinical Practice: Consolidated Guideline and other generally accepted standards of good clinical practice); and all applicable federal, state and local laws, rules and regulations relating to the conduct of the clinical trial.

10.4 Compliance with Trial Registration and Results Posting Requirements

Under the terms of the Food and Drug Administration Modernization Act (FDAMA) and the Food and Drug Administration Amendments Act (FDAAA), the Sponsor of the trial is solely responsible for determining whether the trial and its results are subject to the requirements for submission to the Clinical Trials Data Bank, <http://www.clinicaltrials.gov>. Information posted will allow subjects to identify potentially appropriate trials for their disease conditions and pursue participation by calling a central contact number for further information on appropriate trial locations and trial site contact information.

10.5 Quality Management System

Following the regulations of NTUH

10.6 Data Management

All available data will be displayed. Listings of patients with premature termination will be provided with the dates and reasons for termination. Missing data will not be replaced by any estimated or imputed values.

11.0 APPENDICES

11.1 ECOG Performance Status

Grade	Description
0	Normal activity. Fully active, able to carry on all pre-disease performance without restriction.
1	Symptoms, but ambulatory. Restricted in physically strenuous activity, but ambulatory and able to carry out work of a light or sedentary nature (e.g., light housework, office work).
2	In bed <50% of the time. Ambulatory and capable of all self-care, but unable to carry out any work activities. Up and about more than 50% of waking hours.
3	In bed >50% of the time. Capable of only limited self-care, confined to bed or chair more than 50% of waking hours.
4	100% bedridden. Completely disabled. Cannot carry on any self-care. Totally confined to bed or chair.
5	Dead.

* As published in Am. J. Clin. Oncol.: *Oken, M.M., Creech, R.H., Tormey, D.C., Horton, J., Davis, T.E., McFadden, E.T., Carbone, P.P.: Toxicity And Response Criteria Of The Eastern Cooperative Oncology Group. Am J Clin Oncol 5:649-655, 1982.* The Eastern Cooperative Oncology Group, Robert Comis M.D., Group Chair.

